The PDCSs will gather data from the participants for the contact information, the participant data sheet and the survey orally and enter the answers directly into password-protected tablet. If the tablet is able to be connected to wireless internet at the location, then the data will be entered directly into the secure UNM REDCap data storage system using a database created specifically for this project. BMI data will also be entered into the tablet. If there is no wireless internet connection at the data collection point, the PDCS will upload the data when there is. If entering the data onto the tablet is not possible for some reason, the PDCS will use paper copies of the instruments and later the responses will be double data entered by the Project Coordinator and the Co-PI into REDCap, where the Data Manager will conduct a double data entry analysis to ensure quality.

Blood will be gathered for A1c testing and labeled with the PID. Blood samples will be transported in a padded biohazard transport bag. They will be stored at room temperature at One Hope Clinic in a locked office. Three times a week, the Patient Engagement Coordinator will deliver the blood samples to the UNM CTSC lab for testing. Following testing, the lab will destroy the blood samples using standard laboratory protocol. Results of the blood testing will be sent to both the PI and the Data Manager in hard copy (the results sheet will not include any identifying information, only the PID). The PI will ensure that the Data Manager has entered the results into the database, and then the hard copies of results will be stored in a locked filing cabinet in the Data Manager's locked office for three years (for quality check purposes) when it will be destroyed.

The PDCS will use scissors to collect a pencil lead-width of hair from the crown of the head. One centimeter of hair closest to the scalp will be used to measure hair to determine the average cortisol level

PROTOCOL TITLE: Comparing Program Options for Latinos with Diabetes

over the previous month. The hair will be placed in a plastic bag and labeled with the PID. Hair samples will be stored in a plastic bag in a cool, locked drawer in the office of the PI. When we obtain funds for analysis, hair will be pulverized in a Retsch Mixer Mill Type MM 400 100-240V 50/60HZ, extracted in methanol overnight, dried and resuspended in buffer. Cortisol concentration is measured by an immunoassay or by high-pressure liquid chromatography. Control samples containing specific amounts of cortisol are provided by the vendor with each assay kit, and we also use an internal control. We will use an automated colorimetric 96-well plate reader to measure the results. Cortisol levels are compared with average levels from normal subjects.

Interview and focus group data will be gathered using a small, hand-held electronic audio recorder. Audio-recordings will be uploaded as MP3 files onto the computer of the Research Manager. The Research Manager will upload the MP3 audiofiles into a secure electronic file for transmission to the transcriptionist/translator contractor. The transcriptionist/ translator contractor will download the audio recording. Following transcription/translation, the contractor will destroy the copy of the audiofile and send the transcript to the Research Manager as an email attachment. Once the Research Manager receives the transcript, the original audiofile on the Research Manager's computer will be destroyed.

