11.0 Data Management* and Confidentiality

11.1 *Describe the data analysis plan, including any statistical procedures.*

Descriptive statistics will be calculated to summarize patient characteristics. Means and standard deviations or medians and quartiles will be calculated for continuous variables and will be compared across site by ANOVA or Kruskal-Wallis test, depending on the distribution of the data. Frequencies and percentages will be calculated for categorical variables and will be compared with the chi-square test or Fisher's exact test, as appropriate. Significant differences will be noted and to adjust for possible confounding, those variables will be considered for inclusion as covariates in the analyses for the primary and secondary outcomes in addition to other clinically meaningful variables and their interactions. We expect patient characteristics to be similar across the two treatment sites; however, to control for potential differences in the populations, we will adjust for potential confounding covariates by using propensity scores to stratify subjects into groups based on the probability that they attended a particular treatment site given particular demographic characteristics including sex, age, primary language, level of education, nativity, and type of insurance. Patients will be grouped by quintile of propensity score for a total of five strata and each will be analyzed for the primary and secondary outcomes independently. Analyses will be performed in standard statistical software such as SAS 9.4, R 3.1, and/or Stata 14. Propensity score matching allows for causal inference in our non-experimental settings by selecting similar subsets of comparison units between treatment groups across a high-dimensional set of pretreatment characteristics.

We will complement our quantitative analyses by conducting a rigorous, disciplined, empirical analysis of data from key staff/provider interviews (Aim #1), patient/social support interviews and focus groups (Aims #1 & 2), and Patient Advisory Board interview transcripts.

PROTOCOL TITLE: Comparing Program Options for Latinos with Diabetes

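### Baseline significance tests between sites are one route for nominating outcome-model covariates, and strong prognostic variables outside the named propensity list may depend on that route

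*Combined protocol and SAP*

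**What the plan says.** Section 11.1 of the combined protocol and SAP sets out the adjustment strategy.

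- **Baseline tests.** Continuous variables are "compared across site by ANOVA or Kruskal-Wallis test, depending on the distribution of the data". Categorical variables "will be compared with the chi-square test" or Fisher's exact test. No significance level is given.
- **Test-based nomination.** "Significant differences will be noted and to adjust for possible confounding, those variables will be considered for inclusion as covariates" in the primary and secondary outcome analyses.
- **A route without a test.** The same sentence goes on: "in addition to other clinically meaningful variables and their interactions". These variables are not named, and there is no rule for moving a variable from considered to included.
- **Propensity score.** It models the probability of attending a site "given particular demographic characteristics including sex, age, primary language, level of education, nativity, and type of insurance". These six enter whatever their p-values. "Patients will be grouped by quintile of propensity score for a total of five strata".

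Two other places name covariates without a test. The Aim 3 text of section 11.1 lists, for the A1c model, demographics, social support, knowledge, hair cortisol and CAHPS-CC scores, with BMI and depression handled similarly. Section 11.2 bases its power calculation on regression models with demographics, CAHPS-CC and the social supports' change scores.

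**The concern.** Patients are not randomized. They reach the two programs by different recruitment paths (section 3.1), and sections 1.1 and 9.1 rely on statistical adjustment to deal with self-selection. The choice of covariates therefore carries much of the weight of the comparison.

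Confounding by a variable depends on how far the sites differ on it and how strongly it predicts the outcome. A baseline p-value reflects the first of these mixed with sample size, and says nothing about the second. A strong predictor with a modest, non-significant imbalance can be passed over and still bias the site effect. A variable that differs significantly but does not predict the outcome can be nominated and contribute only noise. Because neither the clinically meaningful variables nor the inclusion rule is stated, the final adjustment set is settled only after the baseline data have been seen.

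**Working it through.** **Inputs from section 11.2.** 120 patients per site enrolled, 20% attrition, 96 per site complete. Check: 120 × 0.80 = 96, which reproduces the plan. The planned effects in SD units are A1c 0.5/1.0 = 0.50, BMI 1.5/3 = 0.50, PHQ-9 3/6 = 0.50, DKQ 2.2/3.8 = 0.58 and PAM-13 12.7/24.8 = 0.51.

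**Assumptions, not in the documents.** Two-sided alpha of 0.05 for the baseline tests, with 0.10 as an alternative; SMDs of 0.20 to 0.30 as imbalances of interest; a correlation r of 0.3 to 0.5 between the omitted variable and the outcome, given the variables already adjusted for.

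**Step 1: how often the screen flags an imbalance.** ANOVA with two groups is the two-sided t-test. With n per site, df = 2n − 2 and noncentrality SMD × √(n/2). For n = 120 and SMD 0.20 the noncentrality is 0.20 × √60 = 1.55, against a critical value of 1.97.

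| True SMD | Flagged, alpha 0.05 | Missed, alpha 0.05 | Missed, alpha 0.10 |
|---|---|---|---|
| 0.20 | 33.9% | 66% | 54% |
| 0.25 | 48.8% | 51% | 39% |
| 0.30 | 63.9% | 36% | 25% |
| 0.40 | 87.0% | 13% | 7% |
| 0.50 | 97.1% | 3% | 1% |

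At alpha 0.05 the 50% point is SMD 0.254, and 80% detection needs SMD 0.363. If the tests were run on the 96 completers per site, the misses at 0.20, 0.25 and 0.30 would be 72%, 59% and 46%. Binary variables behave alike: 50% versus 60% is flagged 34% of the time, and 50% versus 65% is flagged 65% of the time.

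**Step 2: what an omitted variable does to the site effect.** In outcome SD units, bias ≈ SMD × r.

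- Low end: 0.20 × 0.3 = 0.06 SD; 0.06/0.50 = 12% of a planned 0.5 SD effect.
- High end: 0.30 × 0.5 = 0.15 SD; 0.15/0.50 = 30%.
- Weak predictor, r = 0.1: 0.02 to 0.03 SD, or 4% to 6%.

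The high end needs a qualification. At 120 per site and alpha 0.05, an observed SMD reaches significance at 1.97 × √(2/120) = 0.254. A single variable that escaped the test in the enrolled sample therefore contributes at most 0.254 × 0.5 = 0.127 SD there, or 25%. Several such variables can add up, and the imbalance among completers can differ from that at enrollment.

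**Step 3: which variables lack protection.** Set against the six propensity variables, the following are not named: baseline DKQ, PAM-13, PHQ-9 and BMI; baseline A1c; diabetes versus pre-diabetes; and income. Section 3.2 admits patients from pre-diabetes (A1c 5.7, or 5.5 on the study assay) upward, with no upper A1c limit, and incomes up to 250% of the federal poverty level. There is room for the sites to differ. The propensity list is open-ended, so these variables could be added, but nothing commits the team to that.

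**The case against.** The strongest reply is that the tests are not the main adjustment. Significance leads only to consideration, clinically meaningful variables may enter without a test, six demographics are protected by the propensity score, and further covariates are named for the A1c model and in the power section. A reader might infer from the quoted sentence that confounders are picked by significance tests alone. The documents do not support that, and a variable that fails the test can still enter another way.

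A reader might also infer that the screen misses most moderate imbalances. That holds only up to an SMD of about 0.25 at alpha 0.05. At 0.30 most are flagged, and at alpha 0.10 most are already flagged at 0.25.

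Third, a reader might conclude that the confidence intervals are invalid because they ignore the selection step. The screen uses site and baseline data, not follow-up outcomes, so it is not an outcome-driven model search. The issue is omitted-variable bias.

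The reply also has force on particular variables. Income is range-restricted by eligibility. In the A1c model, baseline is one of four modelled time points with a site-by-time interaction, so a baseline site difference in A1c is represented there, and BMI and PHQ-9 are handled similarly. Adjusting change scores for baseline in non-randomized groups is itself debated.

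What does not stand is that the other routes close the gap. The clinically meaningful variables are unnamed. CAHPS-CC is not collected at baseline (section 9.2), so it cannot stand in for a baseline confounder. Knowledge is named in the A1c model without a visit. The covariates in section 11.2 include no baseline outcome score of the patient.

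**Conclusion.** The concern holds in a limited form. A stated rule nominates outcome-model covariates by baseline significance in a non-randomized comparison, and neither the final list nor the inclusion rule is fixed. At this sample size, non-significance is weak evidence of balance for SMDs of 0.20 to 0.30. If a prognostic variable is left out on that ground, the plausible distortion is about 0.06 to 0.15 SD, which is not negligible beside planned effects of 0.50 to 0.58 SD but would not by itself account for an effect of that size.

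The miss rates rest on the assumed alpha, and the bias figures on the assumed correlation. With r near 0.1 the distortion is small. Nothing in the documents shows that any particular confounder will be omitted. The finding is that the plan does not prevent it for several of the variables most likely to predict outcome.

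**What to change.** 1. Delete the rule that nominates covariates by baseline significance.
2. Before any outcome analysis, fix one covariate and propensity list on prognostic grounds. Keep the six named demographics and add baseline A1c, diabetes versus pre-diabetes status, the baseline score of the outcome concerned, and income.
3. Retain every variable on the list regardless of its p-value. Name any further clinically meaningful variables and interactions, or drop that clause.
4. Describe site balance by standardized differences instead of tests.
5. Because baseline adjustment of change scores is debated in this design, report the site effect with and without the baseline outcome score as a sensitivity analysis.

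Two practical checks go with this. Confirm that income is recorded as an amount or in bands, and not only as meeting the eligibility limit. Reconcile sections 9.2 and 11.5 on where baseline A1c comes from: one has the study team draw blood at baseline, the other takes the hospital program's values from its files. The plan itself reports a 0.2 difference between laboratories, so a source that differs by site would undermine baseline A1c as a covariate.

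The cost is SAP wording, a few degrees of freedom out of 2 × 96 = 192 completers, and one extra sensitivity analysis. The baseline scores, A1c and BMI are already due to be collected.

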Patients will be screened by a member of the research team. Patients will be adults (men and women) who have been identified by a provider as having pre-diabetes (A1c 5.7-6.4) or diabetes (A1c 6.5 or above) and: 1.) Enter one of the two diabetes programs during the study; 2.) Self-identify as “Latino;” 3.) Can identify a social support or key member of their social network who will agree to participate with them; 4.) Are not pregnant (participants who become pregnant during the study will be excluded); and 5.) Have household income 250% of the FPL or below. Participants who become pregnant during the study will be excluded. Additionally, we have discovered that there is a difference between the A1c test that CTSC runs and the test run at Quest or TriCore. The test CTSC uses is reliably .2 lower and this is cited in the literature. Therefore, it is appropriate for us to enroll individuals who have a test at another lab that shows them to be pre-diabetic (A1c 5.7-6.4) even if our baseline lab comes back lower (5.5-6.2). However, any individual whose blood gathered by our data collectors at baseline returns with an A1c below 5.5 will be disenrolled.

Social supports will be adult individuals who are identified by the patient participants and who agree to participate.

Advisory Board Members will be seven members of our Project Patient Advisory Board.

PROTOCOL TITLE: Comparing Program Options for Latinos with Diabetes

3.3 Indicate specifically whether you will include or exclude each of the following special populations: (You may not include members of the above populations as subjects in your research unless you indicate this in your inclusion criteria.)

1. *Adults unable to consent*
2. *Individuals who are not yet adults (infants, children, teenagers)*
3. *Pregnant women*
4. *Prisoners*

We will not recruit:

- Adults unable to consent
- Individuals who are not yet adults (infants, children, teenagers)
- Prisoners
- Pregnant women.

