9.0 Procedures Involved*

9.1 Describe and explain the study design.

This project adheres to PCORI methodological standards. Patient-reported outcomes measured with validated and reliable instruments will be the basis for us to compare the effectiveness of two distinct evidence-based models for culturally competent diabetes health promotion through research with two diabetes self-management programs that each currently serve a large Latino patient population from low-income households in Albuquerque, New Mexico. Data will be gathered at baseline, and 3, 6, and 12 months by paid PDCSs (PDCSs) from the target patient population who will be members of the research team. *A priori*, we believe patient populations for each program will be similar, yet we will compare sample characteristics and assess treatment differences after adjusting for possible population differences including the use of propensity scores in our statistical models to mitigate self-selection bias, possible confounding, and heterogeneity of treatment effects. Trickett's conceptualization of "cultural situated-ness" discussed above provides the theoretical framework for this study.^{37,38} We follow National Institutes of Health (NIH) standards for mixed method research set by Creswell and colleagues³⁹ in our "embedded mixed method" research approach, integrating data from quantitative and qualitative components of the study in an iterative fashion.³⁹ Our quasi-experimental research design with pre-/post-testing will accommodate the fact that we are working with existing programs at two sites and that we will recruit patients who enter those programs during the study.⁴⁰ Our sample size (N=240) and power estimates are based on realistic evaluation of effect size. We provide a detailed project timeline with specific deliverables that include scientific and engagement milestones. We have assembled a research team with the expertise and experience in patient-engaged research necessary to conduct the proposed study and we have an institutional infrastructure that supports our academic and community partnerships.

9.2 Provide a description of all research procedures being performed and when they are performed, including procedures being performed to monitor subjects for safety or minimize risks.

Data Collection.

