We will create a database with all interview and focus group transcripts. We will conduct a theory-driven qualitative content analysis. We will read through transcripts to identify conceptual categories and patterns related to specified domains of inquiry, create a qualitative codebook, and develop conceptual summaries for each transcript. Following review and summary, we will code transcripts for systematic themes and sub-themes within the domains. We will explore interconnections between theme categories and develop a holistic interpretation of the data.

Statistical Analysis Aim 3. We will conduct analyses to assess successful patient management of their diabetes (Aim #3), our secondary outcomes, by measuring their A1c from blood samples drawn, BMI calculations, cortisol from hair samples, and PHQ-9 scores obtained at baseline, 3, 6, and 12 months. Clinical analysis of blood samples will use A1c tested on whole blood as described previously. Change in A1c over the four time points in each of the diabetes self-management program models will be evaluated by fitting a linear mixed model to A1c with the primary independent variable treatment site while adjusting for demographic covariates, social support and knowledge, the measures hair cortisol indicating stress levels, and participant and social support scores on the CAHPS-CC. An interaction between time and site will be included to explore how A1c scores change over time. For the secondary endpoint analysis, REML-adjusted least-squares mean estimates of change in A1c from baseline to 6 months post-intervention will be reported along with their 98.3% confidence intervals (the significance level includes a Bonferroni adjustment for three secondary outcomes). A model incorporating the 12 month time point will also be evaluated. BMI and depression scores will be analyzed similarly.

11.2 Provide a power analysis.

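### Baseline disease severity and baseline outcome scores are not pre-specified as adjustment variables in a non-randomised two-site comparison

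*Combined protocol and SAP*

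**What the plan says.** The comparison is between two existing programs that patients enter for themselves. Section 9.1 relies on "propensity scores in our statistical models to mitigate self-selection bias, possible confounding, and heterogeneity of treatment effects". Section 11.1 bases the score on "particular demographic characteristics including sex, age, primary language, level of education, nativity, and type of insurance" and then states: "Patients will be grouped by quintile of propensity score for a total of five strata". It adds that propensity matching selects similar subsets "across a high-dimensional set of pretreatment characteristics".

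There is a second route to adjustment. Section 11.1 compares patient characteristics between sites and says of those that differ significantly: "those variables will be considered for inclusion as covariates in the analyses for the primary and secondary outcomes in addition to other clinically meaningful variables". None of these further variables is named, and none is mandatory.

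The A1c mixed model in 11.1 is fitted "while adjusting for demographic covariates, social support and knowledge, the measures hair cortisol indicating stress levels", plus CAHPS-CC scores and a time-by-site interaction. It reports "REML-adjusted least-squares mean estimates of change in A1c from baseline to 6 months post-intervention", and BMI and depression are to be handled similarly. For DKQ and PAM-13, the only regression described is the one behind the power in 11.2. Its covariates are demographics, CAHPS-CC and the social supports' change scores.

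Section 3.2 admits both pre-diabetes (A1c 5.7 to 6.4) and diabetes (6.5 or above).

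**The concern.** Severity could plausibly differ by site. Under section 3.1, CDE-UNMH patients are approached when they register for an education program. One Hope patients are approached when they call the clinic about diabetes, or after a visit at which a provider ordered an A1c check or gave a diagnosis. A patient who enters with pre-diabetes has less room for A1c to fall than one who enters with a high value. A different mix of the two groups could therefore produce a difference in change between sites with no program effect. The same reasoning applies to patients who enter with low knowledge or activation scores or high depression scores.

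Sex, age, language, education, nativity and insurance may be only loosely related to these quantities. If so, balance on the named variables would not bring balance on severity, and the residual difference would be read as a program effect.

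**Working it through.** **Inputs from section 11.2.** Evaluable n = 96 per site (120 recruited, 20% attrition). A1c: difference 0.5, SD of change 1.0, two-sided alpha 0.017, stated power 84%. DKQ: 2.2, SD 3.8. PAM-13: 12.7, SD 24.8. Both primary outcomes are shown at alpha 0.025, the level printed with their power figures; 11.2 also mentions 0.0125.

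**Assumptions not in the documents.** The baseline-to-6-month correlation rho, the baseline imbalance between sites, equal SDs at the two visits, and both sites regressing to a common mean.

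**Step 1: the plan's own figure.** The standard error of the A1c difference is 1.0 × √(2/96) = 0.144, so the planned effect is 0.5/0.144 = 3.46 standard errors. The critical value at 0.017 is 2.39. Power is 85.9% by the normal approximation and 85.4% by the noncentral t. It is 83.7% with the stated effect size of 0.06 taken as f². The 84% is reproduced.

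**Step 2: bias left in a change score.** The SD of change equals the baseline SD × √(2(1 − rho)). At rho = 0.5 and SD of change 1.0, the baseline A1c SD is 1.0/√1 = 1.0. Under the assumptions above, the spurious difference is (1 − rho) × baseline imbalance.

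| Outcome, rho = 0.5 | Imbalance | Spurious difference | Share of planned effect | False-positive rate (nominal) |
|---|---|---|---|---|
| A1c | 0.25 SD | 0.125 | 25% | 6.5% (1.7%) |
| A1c | 0.5 SD | 0.25 | 50% | 25.6% (1.7%) |
| DKQ | 0.25 SD | 0.475 | 22% | 8.5% (2.5%) |
| DKQ | 0.5 SD | 0.95 | 43% | 30.5% (2.5%) |
| PAM-13 | 0.25 SD | 3.1 | 24% | 8.5% (2.5%) |
| PAM-13 | 0.5 SD | 6.2 | 49% | 30.5% (2.5%) |

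For A1c, as rho goes from 0.3 to 0.8, a 0.25 SD imbalance gives 30% down to 16% of the planned effect (false-positive rate 8.7% down to 3.5%). A 0.5 SD imbalance gives 59% down to 32% (36.8% down to 9.9%).

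**Step 3: would the significance screen catch it?** The plan states no level for the screen. Assume 0.05, 120 per site, and that baseline A1c is among the characteristics compared. A 0.25 SD imbalance has z = 0.25/√(2/120) = 1.94, so it is missed about half the time. A 0.5 SD imbalance has z = 3.87 and would probably be flagged.

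**Step 4: do the listed covariates close the gap?** Section 9.2 collects CAHPS-CC only at 3, 6 and 12 months, so it cannot adjust for differences that precede the program. Knowledge is listed in the A1c model without a time point. Baseline A1c enters that model only as one of the repeated outcomes, and the time-by-site contrast is then a difference in change. Diabetes status appears nowhere.

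**Step 5: does adjustment cost power?** With the patient's baseline value as a covariate, the residual SD is the baseline SD × √(1 − rho²). At the same n and alpha, A1c power is then 97%, 95%, 92% and 90% for rho of 0.3, 0.5, 0.7 and 0.8, ignoring precision lost to site imbalance.

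**The case against.** A reader might infer that baseline severity stays uncontrolled. The documents do not support that. The list is introduced by a word that leaves it open. Section 11.1 has a discretionary covariate route, and sections 1.1 and 9.1 promise adjustment within the statistical models. The change analyses already remove the difference in starting level. All of this stands. What is left is regression to the mean, severity-dependent response, and the fact that nothing binds the team to adjust for either.

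A reader might also infer that the bias could equal the whole planned A1c effect. At rho = 0.5 that needs a 1.0-point imbalance, which is a full baseline SD. With 120 per site, z is about 7.7, and the plan's own site comparison would show it. The team would have to see it and do nothing.

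The phrase about a high-dimensional set could be taken as a false claim of balance. It is better read as a general remark about what matching permits, although the six named variables give it little support.

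Finally, (1 − rho) × imbalance is bias only if both sites regress to a common mean. If the two site populations have stable, different means, the change score can be the unbiased estimate. That objection is sound, and the documents cannot settle it. It makes the figures illustrative; it does not remove the need to decide the adjustment in advance.

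**Conclusion.** The point holds in this form: diabetes versus pre-diabetes status and the patient's own baseline scores are named neither in the propensity model nor among the outcome-model covariates. Their inclusion depends on a p-value screen or on a later choice. In a self-selected comparison with different entry routes and a mixed case load, that is a weakness in a stated method and not just missing detail.

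The exposure is greatest for moderate imbalance, which the screen can miss: at 0.25 SD and rho 0.5, roughly a quarter of the planned effect on A1c, DKQ and PAM-13. Larger imbalances would do more harm but would probably be seen. All sizes rest on the assumed rho, imbalance, equal SDs and common mean. The plan should be changed on this point, but the text does not show that its results will be biased.

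**What to change.** **First, reconcile the source of baseline A1c.** Section 11.5 takes it from program files for CDE-UNMH patients. Section 9.2 has study staff draw blood at baseline for testing at the CTSC lab, and says that the CTSC test reads 0.2 lower than two other laboratories. If the file values came from those laboratories (an assumption), CDE-UNMH would show a spurious fall of 0.2, which is 0.2/0.5 = 40% of the planned difference. A covariate measured differently by site would carry that artefact into the adjustment.

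**Then, in section 11.1:**
- Name diabetes versus pre-diabetes status and baseline A1c, BMI, PHQ-9, DKQ and PAM-13 in the propensity model, as mandatory outcome-model covariates, or both. Add household income if the value is recorded; the documents state only the eligibility ceiling.
- Check balance within strata by standardised differences, before any outcome analysis, in place of p-value screening.

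**Cost.** Apart from possibly income, the measures are already scheduled at baseline, so once the A1c source is settled the change is one of wording. Less overlap between the sites may become visible. More covariates would also be fitted with about 38 to 48 patients per stratum (192/5 to 240/5).
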